**Table 14.2.1.1.16: Time to ACR20 response: Exploratory pairwise comparisons among the dose groups within each regimen**

Cox proportional hazards regression model. Factors in the model are: treatment, region, and previous use of biologics. Placebo won't be used, so can be omitted from the overall model.

The table will present per group: p-value for pairwise comparison versus the other GLPG0634 groups. These p-values will be presented both as uncorrected p-values, and are derived as contrasts within the overall model. As this is a purely exploratory analysis, no adjustment for multiplicity will be performed.

The "raw" SAS PROC output must be provided in a statistical appendix listing.

Population: ITT.

**Table 14.2.1.1.17: Time to ACR20 response: Exploratory pairwise comparisons between regimens within each daily dose level**

Cox proportional hazards regression model. Factors in the model are: regimen, dose, regimen\*dose interaction, region, and previous use of biologics. Placebo subjects will not be used in this model (as there is no q.d./b.i.d. regimen available for placebo). The regimen\*dose interaction will be removed from the final model when not significant at level 0.10 (two-sided type-III p-value). Regimen will have 2 categories: q.d. or b.i.d. Dose will have 3 categories, corresponding to the total daily dose: 50 mg/day, 100 mg/day, or 200 mg/day.

The table will present per group: p-value for pairwise comparison of q.d. versus b.i.d. These p-values will be presented both as uncorrected p-values, and are derived as contrasts within the overall model. As this is a purely exploratory analysis, no adjustment for multiplicity will be performed.

The "raw" SAS PROC output must be provided in a statistical appendix listing.

Population: ITT.

**Table 14.2.1.1.18: Time to ACR50 response: Summary with overall p-value and pairwise comparisons versus placebo**

Repeat table of the ACR20 table.

Population: ITT.

**Table 14.2.1.1.19: Time to ACR50 response: Exploratory pairwise comparisons among the dose groups within each regimen**

Repeat table of the ACR20 table.

Population: ITT.

**Table 14.2.1.1.20: Time to ACR50 response: Exploratory pairwise comparisons between regimens within each daily dose level**

Repeat table of the ACR20 table.

Population: ITT.

**Table 14.2.1.1.21: Time to ACR70 response: Summary with overall p-value and pairwise comparisons versus placebo**

Repeat table of the ACR20 table.

Population: ITT.

**Table 14.2.1.1.22: Time to ACR70 response: Exploratory pairwise comparisons among the dose groups within each regimen**

Repeat table of the ACR20 table.

Population: ITT.

**Table 14.2.1.1.23: Time to ACR70 response: Exploratory pairwise comparisons between regimens within each daily dose level**

Repeat table of the ACR20 table.

Population: ITT.

### **8.1.3. Figures over the whole 24 weeks period**

**Figure 14.2.1.1.1: ACR20/50/70: Plot per week**

Vertical bar chart of the ACR20, ACR50 and ACR70 response rates for the 7 treatment groups. Separate plot per week.

The plot will show two methods of imputing missing values: LOCF and NRI.

Population: ITT.

**Figure 14.2.1.1.2: ACR20: Plot over time**

Line plot of the ACR20 response rates, with a separate line for each of the 7 treatment groups.

The plot will show two methods of imputing missing values: LOCF and NRI.

Population: ITT.

**Figure 14.2.1.1.3: ACR50: Plot over time**

Same plot for the ACR50 response.

The plot will show two methods of imputing missing values: LOCF and NRI.

Population: ITT.

**Figure 14.2.1.1.4: ACR70: Plot over time**

Same plot for the ACR70 response.

The plot will show two methods of imputing missing values: LOCF and NRI.

Population: ITT.

**Figure 14.2.1.1.5: ACR-N: Plot over time**

Mean (without SE) plot of the ACR-N, with a separate line for each of the 7 treatment groups. LOCF only.

Population: ITT.

**Figure 14.2.1.1.6: Time to ACR20 response: Kaplan-Meier plot**

Ascending Kaplan-Meier plot per treatment group.

Population: ITT.

**Figure 14.2.1.1.7: Time to ACR50 response: Kaplan-Meier plot**

Ascending Kaplan-Meier plot per treatment group.

Population: ITT.

**Figure 14.2.1.1.8: Time to ACR70 response: Kaplan-Meier plot**

Ascending Kaplan-Meier plot per treatment group.

Population: ITT.

**8.1.4. Tables after Week 12**

Tables will present only Weeks 12-16-20-24, unless specified otherwise. Tables will show the 15 arms of the “third efficacy analysis chapter”.

**Table 14.2.1.1.24: ACR20 after Week 12: Frequency table**

Frequency table per time point, and per treatment group (15 arms).

The table will show:

- NRI in ITT
- LOCF in ITT
- observed-case in ITT (weeks 12 + 24)

**Table 14.2.1.1.25: ACR50 after Week 12: Frequency table**

Repeat table of the ACR20 table.

The table will show:

- NRI in ITT
- LOCF in ITT
- observed-case in ITT (weeks 12 + 24)

**Table 14.2.1.1.26: ACR70 after Week 12: Frequency table**

Repeat table of the ACR20 table.

The table will show:

- NRI in ITT
- LOCF in ITT
- observed-case in ITT (weeks 12 + 24)

**Table 14.2.1.1.27: ACR-N after Week 12: Descriptive statistics**

Descriptive statistics per time point, and per treatment group (15 arms).

Frequency at Weeks 12 and 24: per treatment group (15 arms). ACR-N will be presented in the following categories:

<10,  
[10,20[,  
[20,30[,  
[30,40[,  
[40,50[,  
[50,60[,  
[60,70[,  
[70,80[,  
[80,90[,  
[90,100].

The table will show:

- LOCF in ITT
- observed-case in ITT (weeks 12 + 24)

**8.1.5. Figures after Week 12**

No figures planned.

## 8.1.6. Listings

### Listing 16.2.6.1: ACR20, ACR50, ACR70 and ACR-N

Listing per treatment group, per subject and per time point of the ACR20/50/70 and ACR-N and their components.

Population: ITT.

## 8.2. EULAR REMISSION

### 8.2.1. Parameters

EULAR remission:

- “YES” when  $TJC28 \leq 1$  and  $SJC28 \leq 1$  and  $CRP \leq 1$  mg/dL and patient’s global assessment of disease activity  $VAS \leq 1$  cm (or 10 mm).
- “NO” when at least 1 of the 4 components has a value  $> 1$ . Note: in case of missing components, it is still possible to qualify as “non remission” if at least 1 of the nonmissing components has a value  $> 1$ .
- “MISSING” in all remaining cases.

If any of the 4 components of the EULAR would be missing, then this missing component will be imputed using the value of the last preceding nonmissing visit.

### 8.2.2. Tables over the whole 24 weeks

Tables will present Baseline-Weeks 1-2-4-8-12-16-20-24. Similar analysis tables as for ACR20 will be made. Analysis population: ITT. NRI, LOCF and observed case (descriptive only at weeks 12 + 24).

**Table 14.2.1.2.1: EULAR remission: Summary with overall p-value and pairwise comparisons versus placebo**

**Table 14.2.1.2.2: EULAR remission: Exploratory pairwise comparisons among the dose groups within each regimen**

**Table 14.2.1.2.3: EULAR remission: Exploratory pairwise comparisons between regimens within each daily dose level**

### 8.2.3. Figures over the whole 24 weeks period

The same bar chart and line plot as for the ACR20 will be made. Population: ITT. NRI and LOCF imputations only.

**Figure 14.2.1.2.1: EULAR remission: Plot per week**

**Figure 14.2.1.2.2: EULAR remission: Plot over time**

## 8.2.4. Tables after Week 12

### Table 14.2.1.2.4: EULAR remission after Week 12: Frequency table

Table will present Weeks 12-16-20-24 for the 15 arms of “efficacy chapter 3”. A similar descriptive analysis as for ACR20 will be performed. Analysis population: ITT. NRI, LOCF and observed case (weeks 12 + 24).

## 8.2.5. Figures after Week 12

No figures planned.

## 8.2.6. Listings

### Listing 16.2.6.2: EULAR remission

Listing per treatment group, per subject and per time point of the EULAR remission category and its components.

Population: ITT.

## 8.3. SDAI AND CDAI SCORES

### 8.3.1. Parameters

$SDAI = TJC28 + SJC28 + \text{patient's disease activity VAS (in cm)} + \text{investigator's disease activity VAS (in cm)} + CRP \text{ (in mg/dL)}$ .

$CDAI = TJC28 + SJC28 + \text{patient's disease activity VAS (in cm)} + \text{investigator's disease activity VAS (in cm)}$ .

(TJC28 and SJC28 are the 28 joint counts for tenderness and swelling. See further sections on how to derive these components.)

CDAI and SDAI scores can only be derived when all components are nonmissing. If any of the components would be missing, then this missing component will be imputed using the value of the last preceding nonmissing visit.

Note that if for a specific visit both the regular CRP as well as the high-sensitive CRP are available, the high-sensitive CRP will be used for the derivation of the SDAI.

Apart from the actual scores, the changes from baseline and percent changes from baseline will be derived.

The SDAI is also categorized:

- High disease activity: SDAI > 26
- Moderate disease activity: SDAI in ] 11 , 26 ]
- Low disease activity: SDAI in ] 3.3 , 11 ]
- Remission: SDAI  $\leq$  3.3

The CDAI is also categorized:

- High disease activity: CDAI > 22
- Moderate disease activity: CDAI in ] 10 , 22 ]
- Mild disease activity: CDAI in ] 2.8 , 10 ]
- Remission: CDAI  $\leq$  2.8

Note that the percentage change from baseline remains missing if the baseline value itself equals zero.

### 8.3.2. Tables over the whole 24 weeks period

Tables will present Baseline-Weeks 1-2-4-8-12-16-20-24, unless specified otherwise.

Analysis population: ITT. LOCF and observed case (descriptive only at Baseline and Weeks 12 + 24).

#### Table 14.2.1.3.1: SDAI and CDAI: Descriptive statistics of the actual values

Descriptive statistics of the actual values per time point, and per treatment group.

Frequency per time point (all time points), and per treatment group. SDAI and CDAI will be presented in the categories defined above (remission, low, moderate, high).

The table will show:

- LOCF in ITT
- observed-case in ITT (Baseline, Week 12 and Week 24 only)

#### Table 14.2.1.3.2: SDAI and CDAI: Descriptive statistics of the change from baseline

Descriptive statistics of the changes from baseline per time point, and per treatment group.

The table will show:

- LOCF in ITT
- observed-case in ITT (weeks 12 + 24 only)

#### Table 14.2.1.3.3: SDAI and CDAI: Descriptive statistics of the percent change from baseline

Descriptive statistics of the percent changes from baseline per time point, and per treatment group.

Frequency table at Weeks 12 and 24 with cumulative percentages of the percent change from baseline, categorized as:

$\geq 0$ ,  
 [ -10 , 0 [,  
 [ -20 , -10 [,  
 [ -30 , -20 [,  
 [ -40 , -30 [,  
 [ -50 , -40 [,  
 [ -60 , -50 [,  
 [ -70 , -60 [,  
 [ -80 , -70 [,  
 [ -90 , -80 [,  
 [ -100 , -90 [.

The table will show:

- LOCF in ITT
- observed-case in ITT (weeks 12 + 24 only)

**Table 14.2.1.3.4: SDAI and CDAI: Summary with overall p-value and pairwise comparisons versus placebo**

ANCOVA model on the change from baseline at each time point. Factors in the model are: treatment, baseline value, region, and previous use of biologics.

Per time point, the table will present:

- Overall type-III p-value for all explanatory factors in the model.
- Per group: difference in LS-means versus the placebo group (GLPG0634 minus placebo), together with a 95% confidence interval of this difference.
- Per group: p-value for pairwise comparison versus the placebo group, derived from contrasts within the overall model. These p-values will be presented both as uncorrected p-values as well as corrected for multiplicity according to Hommel's closed-testing method (SAS PROC MULTTEST).

The "raw" SAS PROC output must be provided in a statistical appendix listing.

The table will show:

- LOCF in ITT

Table to be created for the Week 12 interim analysis as well, cut off at Week 12.

**Table 14.2.1.3.5: SDAI and CDAI: Exploratory pairwise comparisons among the dose groups within each regimen**

ANCOVA model on the changes from baseline at each time point. Factors in the model are: treatment, baseline value, region, and previous use of biologics. Placebo won't be used, so can be omitted from the overall model.

Per time point, the table will present:

- Per group: difference in LS-means versus the other GLPG0634 groups within the same regimen (q.d. or b.i.d.), together with a 95% confidence interval of this difference.
- Per group: p-value for pairwise comparison versus the other GLPG0634 groups. These p-values will be presented both as uncorrected p-values, and are derived as contrasts within the overall model. As this is a purely exploratory analysis, no adjustment for multiplicity will be performed.

The “raw” SAS PROC output must be provided in a statistical appendix listing.

The table will show:

- LOCF in ITT

Table to be created for the Week 12 interim analysis as well, cut off at Week 12.

**Table 14.2.1.3.6: SDAI and CDAI: Exploratory pairwise comparisons between regimens within each daily dose level**

ANCOVA model on the change from baseline at each time point. Factors in the model are: baseline value, regimen, dose, regimen\*dose interaction, region, and previous use of biologics. Placebo subjects will not be used in this model (as there is no q.d./b.i.d. regimen available for placebo). The regimen\*dose interaction will be removed from the final model when not significant at level 0.10 (two-sided type-III p-value). Regimen will have 2 categories: q.d. or b.i.d. Dose will have 3 categories, corresponding to the total daily dose: 50 mg/day, 100 mg/day, or 200 mg/day.

Per time point, the table will present:

- Per dose: difference in LS-means of q.d. versus b.i.d. within the same dose level (50, 100 or 200 mg/day), together with a 95% confidence interval of this difference.
- Per group: p-value for pairwise comparison of q.d. versus b.i.d. These p-values will be presented both as uncorrected p-values, and are derived as contrasts within the overall model. As this is a purely exploratory analysis, no adjustment for multiplicity will be performed.

The “raw” SAS PROC output must be provided in a statistical appendix listing.

The table will show:

- LOCF in ITT

Table to be created for the Week 12 interim analysis as well, cut off at Week 12.

**Table 14.2.1.3.7: SDAI and CDAI remission: Summary with overall p-value and pairwise comparisons versus placebo**

Similar table as for ACR20, presenting the rates of SDAI remission and CDAI remission at Week 12 and Week 24.

The table will show:

- NRI in ITT
- LOCF in ITT

- observed-case in ITT (descriptive at Week 12 + 24; inferential statistics at Week 12 only).

**Table 14.2.1.3.8: SDAI and CDAI remission: Exploratory pairwise comparisons among the dose groups within each regimen**

**Table 14.2.1.3.9: SDAI and CDAI remission: Exploratory pairwise comparisons between regimens within each daily dose level**

### **8.3.3. Figures over the whole 24 weeks period**

LOCF only. Population: ITT.

**Figure 14.2.1.3.1: SDAI and CDAI: Plot of the actual values over time**

Mean (without SE) plot of the actual values over time up to (and including) Week 24, with a separate line for each of the 7 treatment groups.

Population: ITT.

**Figure 14.2.1.3.2: SDAI and CDAI: Plot of the changes from baseline over time**

Mean (without SE) plot of the changes from baseline over time up to (and including) Week 24, with a separate line for each of the 7 treatment groups. With a horizontal reference line at 0, indicating no change.

Population: ITT.

**Figure 14.2.1.3.3: SDAI and CDAI: Plot of the percent changes from baseline over time**

Repeat plot for the percent change.

Population: ITT.

### **8.3.4. Tables after Week 12**

Tables will present Weeks 12-16-20-24, unless specified otherwise, for the 15 arms of “efficacy chapter 3”. A similar descriptive analysis will be performed. Analysis population: ITT. LOCF and observed case (weeks 12 +24).

**Table 14.2.1.3.10: SDAI and CDAI after Week 12: Descriptive statistics of the actual values**

**Table 14.2.1.3.11: SDAI and CDAI after Week 12: Descriptive statistics of the change from baseline**

**Table 14.2.1.3.12: SDAI and CDAI after Week 12: Descriptive statistics of the percent change from baseline**

### **8.3.5. Figures after Week 12**

No figures planned.

### 8.3.6. Listings

#### Listing 16.2.6.3: SDAI and CDAI

Listing per treatment group, per subject and per time point of the SDAI and CDAI scores and their components. SDAI and CDAI: actual values, changes from baseline, percent changes from baseline, and the categorization.

Population: ITT.

## 8.4. DAS28(CRP)

### 8.4.1. Parameters

$$\text{DAS28(CRP)} = 0.56 \times \sqrt{\text{TJC28}} + 0.28 \times \sqrt{\text{SJC28}} + 0.36 \times \text{Ln}[1 + \text{CRP (in mg/L)}] + 0.014 \times \text{patient's disease activity VAS (in mm)} + 0.96$$

(TJC28 and SJC28 are the 28 joint counts for tenderness and swelling. See further sections on how to derive these components. Ln = natural logarithm.)

DAS28(CRP) scores can only be derived when all components are nonmissing. If any of the components of the DAS28(CRP) would be missing, then this missing component will be imputed using the value of the last preceding nonmissing visit.

Note that if for a specific visit both the regular CRP as well as the high-sensitive CRP are available, the high-sensitive CRP will be used for the derivation of the DAS28(CRP).

Note that the percentage change from baseline remains missing if the baseline value itself equals zero.

Next to the actual DAS28(CRP) value, also the changes and percent changes from baseline will be derived.

Categorization of the DAS28(CRP) scores:

- High disease activity: > 5.1
- Moderate disease activity: ] 3.2 , 5.1 ]
- Low disease activity: [ 2.6 , 3.2 ]
- Remission: < 2.6

A second categorization of the DAS28(CRP) into EULAR response categories (none, moderate, good) will be done according to the following:

Actual DAS28(CRP)	Improvement in DAS28(CRP) from baseline:		
	> 1.2	] 0.6, 1.2]	≤ 0.6
≤ 3.2	Good	Moderate	None
]3.2, 5.1]	Moderate	Moderate	None
> 5.1	Moderate	None	None

#### 8.4.2. Tables over the whole 24 weeks period

Tables will present Baseline-Weeks 1-2-4-8-12-16-20-24, unless specified otherwise. A similar analysis as to SDAI and CDAI will be performed. Analysis population: ITT. LOCF and observed case (descriptive at Baseline, Week 12 and Week 24; inferential statistics only at Week 12).

##### Table 14.2.1.4.1: DAS28(CRP): Descriptive statistics of the actual values

(descriptive statistics, including a frequency table at all time points)

Analysis population: ITT and per-protocol.

Table to be created for the Week 12 interim analysis as well, cut off at Week 12. ITT only.

##### Table 14.2.1.4.2: DAS28(CRP): Descriptive statistics of the change from baseline

(descriptive statistics, including a shift table at all time points)

Analysis population: ITT and per-protocol.

Table to be created for the Week 12 interim analysis as well, cut off at Week 12. ITT only.

##### Table 14.2.1.4.3: DAS28(CRP): Descriptive statistics of the percent change from baseline

(descriptive statistics, including a frequency table at Weeks 12 + 24)

Analysis population: ITT and per-protocol.

Table to be created for the Week 12 interim analysis as well, cut off at Week 12. ITT only.

##### Table 14.2.1.4.4: DAS28(CRP): Summary with overall p-value and pairwise comparisons versus placebo

Analysis population: ITT and per-protocol.

Table to be created for the Week 12 interim analysis as well, cut off at Week 12. ITT only.

##### Table 14.2.1.4.5: DAS28(CRP): Exploratory pairwise comparisons among the dose groups within each regimen

Analysis population: ITT and per-protocol.

Table to be created for the Week 12 interim analysis as well, cut off at Week 12. ITT only.

**Table 14.2.1.4.6: DAS28(CRP): Exploratory pairwise comparisons between regimens within each daily dose level**

Analysis population: ITT and per-protocol.

Table to be created for the Week 12 interim analysis as well, cut off at Week 12. ITT only.

**Table 14.2.1.4.7: DAS28(CRP) change from baseline at Week 12: Tabulation versus baseline characteristics**

The table will show LOCF only.

Descriptive statistics of the DAS28(CRP) change from baseline at Week 12 per treatment group, split up according to the following baseline categories:

- Demographics:
  - Region (as used in the central randomization)
  - Country
  - Gender
  - Age categories:
    - < 45 ;
    - [45,65[ ;
    - [65,75[ ;
    - ≥ 75 years
  - BMI categories:
    - ≤ 18.5;
    - ] 18.5 , 25.0 ] ;
    - ] 25 , 30 [,
    - ≥ 30 kg/m^2
- Baseline disease characteristics:
  - Duration of RA:
    - < 1;
    - [ 1 , 2 [ ;
    - [ 2 , 5 [ ;
    - [ 5 , 10 [ ;
    - [ 10 , 20 [ ;
    - ≥ 20 years
  - Baseline CRP:
    - <0.7 x ULN;
    - [0.7,1.0] x ULN;
    - ]1.0,1.2[ x ULN;
    - ≥ 1.2 x ULN
  - Baseline TJC68: < 20, ≥ 20
  - Baseline SJC66: < 20, ≥ 20
  - Baseline DAS28(CRP): high, moderate, low, remission (see further section on DAS28 for the definition of these categories)
  - RF status

- Anti-CCP status
- Previous use of:
  - Biological (anti-TNF or other biological DMARD) yes/no
  - anti-TNF yes/no,
  - other biological DMARD yes/no,
  - conventional DMARD yes/no,
  - NSAID yes/no,
  - steroid yes/no,
  - analgesic yes/no,
  - other RA medication yes/no.

Population: ITT.

Table to be created for the Week 12 interim analysis as well.

**Table 14.2.1.4.8: DAS28(CRP) change from baseline at Week 12: Exploratory ANCOVA model containing baseline characteristics**

The table will show LOCF only.

ANCOVA model of the DAS28(CRP) change from baseline at Week 12, with the following exploratory factors:

- Treatment group
- Demographics:
  - Region
  - Country
  - Gender
  - Age as continuous variable
  - BMI as continuous variable
- Baseline disease characteristics:
  - Duration of RA as continuous variable
  - Baseline CRP as continuous variable
  - Baseline TJC68 and SJC66 as continuous variables
  - Baseline DAS28(CRP) as continuous variable
  - RF status
  - anti-CCP status
  - Previous use of:
    - Biological (anti-TNF or other biological DMARD) yes/no
    - anti-TNF yes/no,
    - other biological DMARD yes/no,
    - conventional DMARD yes/no,
    - NSAID yes/no,
    - steroid yes/no,
    - analgesic yes/no,
    - other RA medication yes/no.

All these factors will be tested using a stepwise selection approach. Significance level to enter the model: 0.10; significance level to stay in the model: 0.05. The treatment groups will always be kept in the model, even when not significant at level 0.05. The table will present only the final model with type-III p-value and LS-mean estimates. The “raw” SAS PROC output must be provided in a statistical appendix listing, and will contain all details on the model building steps.

Population: ITT.

**Table 14.2.1.4.9: DAS28(CRP) remission: Summary with overall p-value and pairwise comparisons versus placebo**

Similar table as for ACR20, presenting the rates of DAS28(CRP) remission at Week 12 and Week 24.

The table will show:

- NRI in ITT
- LOCF in ITT
- observed-case in ITT (descriptive at Week 12 + 24; inferential statistics at Week 12 only).

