This study is not powered for any formal comparison among the dose groups, nor for comparisons between q.d. and b.i.d. regimens. However, differences between q.d. and b.i.d. regimens will be calculated and presented with a 95% confidence interval. Differences between q.d. and b.i.d. regimens will also be tested exploratively via a model containing the total daily dose (50/100/200 mg) as well as the regimen (q.d./b.i.d.). This model will not use the placebo data. Differences among the q.d. groups and among the b.i.d. groups will be described using the same model. No adjustment for multiplicity will be done for these exploratory differences.

Analysis methods per post-baseline time point:

- Binary parameters (such as ACR20): logistic regression model with factors treatment, region and previous use of biologics.
- Continuous parameters: both the changes from baseline and the percent changes from baseline will be described. Formal between-group comparisons will be performed on the changes from baseline only, using an analysis of (co)variance (AN[C]OVA) model with factors treatment, baseline value, region and previous use of biologics. Baseline will be the last nonmissing value prior to first dosing in the study.
- Time to (first) response (ACR20/50/70) will be analyzed using Kaplan-Meier survival techniques, and groups will be compared against placebo using a Cox proportional hazards regression model with factors treatment, region and previous use of biologics.

Quality of Life data (FACIT fatigue scale and SF-36 questionnaire) will be analyzed descriptively. Exploratory between-group comparisons will also be done at each post-baseline time point using AN(C)OVA models on the changes from baseline with factors treatment, baseline value, region and previous use of biologics.

A descriptive sensitivity analysis by baseline characteristic (such as country, geographic region, previous use of biological DMARDs etc) will be performed for the ACR20 response and the change in DAS28(CRP). Additionally an exploratory regression model will be fitted using a stepwise selection algorithm on the ACR20 response and the change in DAS28(CRP) at Week 12, using treatment and baseline characteristics as explanatory factors to investigate which baseline factors have an influence on the response.

Graphical presentations are added to facilitate the overall interpretation of the study results.

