#### **Table 14.2.1.1.1: ACR20: Summary with overall p-value and pairwise comparisons versus placebo**

Logistic regression model at each time point, modeling the responders. Factors in the model are: treatment, region, and previous use of biologics.

Per time point, the table will present:

- Overall type-III p-value for all explanatory factors in the model.
- Per group: number and percentage of responders, difference in percentage responders versus the placebo group (GLPG0634 minus placebo), together with a 95% confidence interval of this difference (as provided by SAS PROC FREQ).
- Per group: p-value for pairwise comparison versus the placebo group, derived from contrasts within the overall regression model. These p-values will be presented both as uncorrected p-values as well as corrected for multiplicity according to Hommel's closed-testing method (SAS PROC MULTTEST).

The "raw" SAS PROC output must be provided in a statistical appendix listing.

The table will show:

- NRI in ITT and in per-protocol
- LOCF in ITT and in per-protocol
- observed-case in ITT (descriptive at Week 12 + 24; inferential statistics at Week 12 only).

Table to be created for the Week 12 interim analysis as well, cut off at Week 12. ITT only.

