**Table 14.2.1.4.10: DAS28(CRP) remission: Exploratory pairwise comparisons among the dose groups within each regimen**

**Table 14.2.1.4.11: DAS28(CRP) remission: Exploratory pairwise comparisons between regimens within each daily dose level**

**Table 14.2.1.4.12: DAS28(CRP) remission and low disease activity: Summary with overall p-value and pairwise comparisons versus placebo**

Similar table as for the remission, but now combining “remission” and “low disease activity” into one percentage.

**Table 14.2.1.4.13: DAS28(CRP) remission and low disease activity: Exploratory pairwise comparisons among the dose groups within each regimen**

**Table 14.2.1.4.14: DAS28(CRP) remission and low disease activity: Exploratory pairwise comparisons between regimens within each daily dose level**

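### The tested remission endpoints and DAS28(CRP) low disease activity copy the ACR20 logistic model, which has no baseline score; adding one would raise power, by an amount that depends on a correlation the documents do not give

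*SAP*

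**What the plan says.** The general rule for binary endpoints in SAP 6.1.2.3 is a "logistic regression model with factors treatment, region and previous use of biologics". The ACR20 template, Table 14.2.1.1.1, repeats it: "Factors in the model are: treatment, region, and previous use of biologics".

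The disease-state tests then point back to that template:

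- **DAS28(CRP) remission** (Table 14.2.1.4.9): "Similar table as for ACR20, presenting the rates of DAS28(CRP) remission at Week 12 and Week 24".
- **DAS28(CRP) remission or low disease activity** (Table 14.2.1.4.12): "Similar table as for the remission, but now combining" the two categories.
- **SDAI and CDAI remission** (Table 14.2.1.3.7): "Similar table as for ACR20, presenting the rates of SDAI remission and CDAI remission at Week 12 and Week 24".
- **ACR/EULAR remission** (SAP 8.2.2): "Similar analysis tables as for ACR20 will be made".

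The continuous SDAI and CDAI analyses (Table 14.2.1.3.4) are different: "Factors in the model are: treatment, baseline value, region, and previous use of biologics". SAP 8.4.2 applies the same approach to continuous DAS28(CRP). Baseline DAS28(CRP), SDAI and CDAI are all listed as derived variables in SAP 7.5.1.

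**The concern.** ACR20 is a percentage improvement from baseline, so the starting level is already part of the endpoint. The endpoints above are absolute states: DAS28(CRP) below 2.6 (or at most 3.2 with low disease activity included), SDAI at most 3.3, CDAI at most 2.8, or four components each at most 1. To reach DAS28(CRP) remission, a subject who enters at 4.5 must fall by about 1.9 and one who enters at 6.5 by about 3.9 (illustrative values). Protocol 8.3.2 sets minimum joint counts but no maximum, so this distance varies between subjects, and the planned model ignores it.

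Leaving a prognostic covariate out of a logistic model pulls the treatment coefficient towards zero and lowers power. It also leaves each comparison open to chance imbalance in baseline activity. Six doses are each compared with placebo at about 85 per arm under a multiplicity correction, so power is worth protecting.

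**Working it through.** **1. The plan's own power figure.** Inputs from protocol 8.8.2: n=85 per arm, α=0.05/6=0.0083 per comparison, chi-square test. Sidedness is not stated; two-sided reproduces the figures.

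Power = Φ{[|p1−p0|√n − z(α/2)·√(2p̄q̄)] / √(p1q1+p0q0)}, with z(α/2)=2.638.

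For 20% v 48%, p̄=0.34: (0.28×9.220 − 2.638×0.670)/0.640 = 1.27, so power is 89.8%. The other three scenarios give 91.3% (40 v 70), 80.9% (20 v 45) and 78.4% (40 v 66). The stated values are 90, 90, 80 and 80%, so the plan's figure is reproduced. It covers ACR20 only; no power is stated for remission or low disease activity.

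**2. Assumptions needed for the disease-state endpoints.** The documents give no expected rates and no baseline-to-Week 12 correlation r. Both are assumed over a range.

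**3. Simulation.** Seven arms of 85, with all six active arms at the same rate. The logistic model has treatment, four regions and prior biologics (10% prevalence assumed), fitted with and without continuous baseline. The endpoint is a latent Week 12 score, correlated r with baseline, falling below a threshold. Wald contrasts against placebo at 0.05/6 two-sided; 1,200-1,500 runs per cell; no dropout. Power in %, without → with baseline:

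| Placebo v active | r=0.2 | r=0.3 | r=0.4 | r=0.5 | r=0.6 |
|---|---|---|---|---|---|
| 7 v 22 | 51.2→52.5 | 51.0→53.8 | 48.6→54.5 | 51.3→59.6 | 50.5→64.5 |
| 10 v 30 | 73.5→74.6 | 73.7→76.2 | 73.3→78.0 | 73.1→81.4 | 71.8→84.7 |
| 20 v 45 | 80.2→81.3 | 80.2→82.8 | 80.0→84.7 | 80.5→88.0 | 80.8→90.7 |
| 20 v 48 | not run | 89.9→91.8 | 90.1→92.9 | 90.3→95.0 | 90.1→96.6 |

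The gains are 1.1-1.3 points at r=0.2, 1.9-2.8 at 0.3, 2.8-5.9 at 0.4, 4.7-8.3 at 0.5 and 6.5-14.0 at 0.6. At r of 0 or 0.1 the change was between −0.2 and +0.4. The unadjusted figure should not vary along a row, so its movement is simulation noise. Each gain compares two models on the same data sets.

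**4. Planned multiplicity procedure.** Hommel rejects at least as often as Bonferroni, so starting power is higher. With all doses effective at 20 v 42%:

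- Bonferroni: 68→71% at r=0.3 and 69→78% at r=0.5.
- Hommel: 82→84% at r=0.3 and 83→89% at r=0.5.

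At 8 v 22% under Hommel the start is 57-59%, and the gain at r=0.5 is about 8 points.

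**5. Rare remission.** At 2 v 8%, power goes from 0.5 to 1.0% at r=0.3 and from 0.7 to 2.6% at r=0.5, and about 20% of runs do not converge. That agrees with the chance of a placebo arm with no events, 0.98^85=0.18. At 3 v 12% it goes from 10.2 to 12.5% at r=0.3 and from 10.0 to 18.0% at r=0.5.

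**6. Type I error.** With 7% in every arm, the per-comparison rejection rate was 0.2% or less in both models. With 20% in both arms of a two-arm run at r=0.5, the two models gave 0.73% and 0.78%. All are below the nominal 0.83%.

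**The case against.** Several points against stand.

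- **Scope.** A reader might infer that low disease activity is tested without baseline on every index. It is not. SDAI and CDAI low disease activity appear only in a frequency table (Table 14.2.1.3.1), and ACR/EULAR has no such category. Only DAS28(CRP) low disease activity is tested.
- **Size.** A reader might infer a definite loss of several points. The documents cannot support that, because rates and correlation are both assumed. The joint-count minimums at Baseline truncate low scores and could lower r; non-responder imputation would also weaken it, and the simulation had no dropout. Week 24 was not simulated.
- **Cost.** A reader might infer that the change is free. Sparse arms may not converge. The displayed difference and interval are unadjusted PROC FREQ output (Table 14.2.1.1.1), so adjusting only the p-value widens an existing mismatch. The model without baseline is also the one in protocol 8.8.1.3. SAP 6.3.2 shows that the DAS28, SDAI and CDAI disease-state tests were added after interim lock, when the sponsor could view unblinded Week 12 summaries (SAP 6.2).
- **Coverage elsewhere.** The continuous scores already get baseline-adjusted, Hommel-corrected tests, and baseline characteristics are tabulated by arm. Randomisation keeps the unadjusted tests valid.
- **Active-only tables.** The power argument against placebo does not reach the exploratory comparisons between doses or regimens. Adjusting there is for consistency.
- **ACR/EULAR remission.** It has no single baseline score. DAS28(CRP) uses the same four measures but is a proxy that has to be chosen.

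None of this removes the inconsistency: the same index is baseline-adjusted as a score and unadjusted as a threshold. Protocol 8.8.1.3 also allows other applicable factors in the models.

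**Conclusion.** The point holds as a modest efficiency issue on secondary endpoints. The five disease-state tests omit a baseline score that the SAP already derives and already uses for the continuous versions of the three indices.

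For the assumed rates in the table, the per-comparison gain under Bonferroni is about 1 point at r=0.2, 2-3 at r=0.3, 5-9 at r=0.5 and up to about 14 at r=0.6. Under Hommel with all doses effective it is about 2 points at r=0.3 and 6-8 at r=0.5. At 2 v 8% it is negligible. A gain of several points therefore needs r of roughly 0.4 or more and remission that is not very rare. There was no sign of type I inflation. The primary ACR20 analysis is untouched.

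**What to change.** Before final database lock:

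1. Add the continuous baseline value of the same index (DAS28(CRP), SDAI or CDAI) to the logistic models in Tables 14.2.1.3.7-9 and 14.2.1.4.9-14.
2. Optionally, add baseline DAS28(CRP) as a proxy in Tables 14.2.1.2.1-3, with the reason for that choice.
3. Record the change and its rationale in SAP 6.3.2, and keep the unadjusted model as a sensitivity analysis.
4. Name a penalised-likelihood fallback for sparse arms.
5. Preferably, show a baseline-adjusted risk difference so that the interval matches the p-value.
6. Leave the ACR20/50/70 models unchanged.

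The cost is one covariate in existing programs, plus the fallback and adjusted difference; no new data are needed. The odds ratio becomes conditional on baseline, which matters little where the tables report p-values and rate differences. Because interim summaries had been available to the sponsor, the documentation in step 3 is essential. If final lock has passed, the adjusted model should be reported only as a labelled post hoc sensitivity analysis.
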